6.3 Analysis Populations

Enrolled Population: includes all subjects enrolled into the study, including subjects in the historical control arm.

Safety Population: includes all subjects enrolled into the study who received any study treatment with RBX2660; this does not include subjects in the historical control arm.

Full Analysis Set (FAS) Population: includes the Safety Population and subjects in the historical control arm.

Evaluable Population: includes the FAS subjects who were evaluable for treatment outcome (e.g., exclude subjects that discontinued from the study prior to determination of treatment failure and were not followed for at least 56 days (day 49 – 63) after the last treatment date).

Per Protocol Population: includes subjects from the Evaluable Population, excluding:

- Subjects from the Safety Population that did not complete 2 enemas

- Subjects that received fecal microbiota transplant before the 8-week follow-up and lacked a documented recurrence of CDI (Treatment Failure eCRF)
- Violations to the inclusion or exclusion criteria, including protocol definition of recurrent CDI two hospitalizations for CDI or 3 recurrent CDI events
- Received prohibited medication during the 8-week follow-up period

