#### 4.3 Subject Recruitment and Screening

Subjects are recruited by qualified and trained site personnel when they are identified as experiencing either a) at least two recurrences of CDI after a primary episode (i.e., at least three episodes) and have completed at least two rounds of standard-of-care oral antibiotic therapy or b) had at least two episodes of severe CDI resulting in hospitalization. Potential subjects are to be fully informed as to this study's purpose, requirements, anticipated risks, etc., and are to be given the chance to review the informed consent form and receive satisfactory answers to all questions. Subjects must then sign the study-specific, IRB/REB-approved Informed Consent Form and HIPAA Form (if applicable), which is the point of study enrollment.

Subjects are eligible to receive study treatment upon confirmation that they have met all inclusion/exclusion criteria listed in Sections 4.1 and 4.2. Subjects must discontinue their antibiotics for 24-48 hours prior to receiving the first study enema.

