**Table 6-2:**

The pre-treatment Subject Diary is reviewed and collected and a post-treatment Subject Diary is given to the subject; completion instructions are to be reviewed with the subject. Inclusion/exclusion criteria and completion of the washout period are confirmed. Recurrence of CDI symptoms is assessed, concomitant medications are recorded and AEs/SAEs are assessed. Prior to administration of each dose of RBX2660, a female subject of childbearing potential is required to undergo a urine-dipstick pregnancy test to confirm that she is not pregnant. RBX2660 is administered via enema per the Instructions for Use and standard site procedure by the authorized RBX2660 Administrator; see section 5.9.3.

[REDACTED]  
[REDACTED]  
[REDACTED] The subject is sent home after a review of the Subject Diary instructions, instructions to call the study coordinator if CDI symptoms reoccur, and an appointment for the next enema of RBX2660.

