**A6. Inclusion / Exclusion Criteria for Historical Control Group**

**A6.1 Inclusion Criteria for Selection of Historical Control Group**

All responses must be “yes” to include a record in the study:

1.  $\geq 18$  years old.
2. Medical record documentation of recurrent CDI including at least one positive *C. difficile* test at the time of original diagnosis and medical record documentation of: a) at least two recurrences after a primary episode and has completed at least two rounds of standard-of-care oral antibiotic therapy or b) has had at least two episodes of severe CDI resulting in hospitalization.

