8 STATISTICAL ANALYSIS

8.1 Disposition of Subjects

A summary table will present subject disposition for all subjects. The table will show the number of RBX2660 treated subjects enrolled and the number of enrolled subjects not treated followed by the number of subjects in the study population as well as the number of historical controls included in the study. [REDACTED]

[REDACTED]

[REDACTED]

Discontinuation will be categorized by reason as a percentage of the number of all subjects in study population.

[REDACTED]

[REDACTED]

[REDACTED]

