8.7 Analysis of Efficacy

8.7.1 Treatment Success

Treatment success is the primary efficacy endpoint and the analyses will be performed on the Evaluable Population. The primary endpoint will be summarized by frequencies and percentages

[REDACTED]

[REDACTED] The analysis of efficacy will be repeated using the Full Analysis Set and Per Protocol populations. Sensitivity analyses will also be conducted using the Full Analysis Set where missing responses are imputed using a best-case scenario where missing responses are treated as successes.

[REDACTED]

[REDACTED]

[REDACTED]

[REDACTED]

[REDACTED]

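### No readable efficacy analysis counts RBX2660 subjects who leave for CDI reasons between enrollment and dosing, and the control criteria set no visible matching starting point

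*SAP*

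**What the plan says.** Protocol 4.3 makes signing consent the act "which is the point of study enrollment". The subject is already on CDI antibiotics or starts them at enrollment (Protocol 4.1, item 3) and stops them 24-48 hours before the first enema (4.3). On the day of that enema, Protocol 6.5 states: "Inclusion/exclusion criteria and completion of the washout period are confirmed". SAP 6.1 likewise marks the eligibility check at both Visit 1 and Visit 2.

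SAP 6.3 then builds the analysis sets in layers:

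- The Safety Population "includes all subjects enrolled into the study who received any study treatment with RBX2660".
- The FAS "includes the Safety Population and subjects in the historical control arm".
- The Evaluable Population "includes the FAS subjects who were evaluable for treatment outcome", and the Per Protocol Population is a subset of it.

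SAP 8.7.1 states: "Treatment success is the primary efficacy endpoint and the analyses will be performed on the Evaluable Population". It repeats the analysis in the FAS and Per Protocol sets and adds a best-case imputation within the FAS. SAP 8.1 tabulates "the number of enrolled subjects not treated", and SAP 8.4 gives baseline summaries for the Enrolled Population.

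For controls, Appendix 1 A6.1 opens its list with "All responses must be “yes” to include a record in the study" and shows two items, age and documented recurrent CDI. A6.2 items 1 and 2 repeat the trial's exclusions for continued diarrhea on CDI antibiotics and for continuous antibiotics for another condition.

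**The concern.** The two arms appear to be counted from different points. An RBX2660 subject contributes to efficacy only after passing through the antibiotic course, the washout and the Visit 2 re-check and then being dosed. A control contributes once the chart is selected, and the readable criteria do not say what state the patient must be in when the analysed course ends.

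If some control failures occur at a stage where the RBX2660 counterpart would have left undosed, they lower the control rate only. The comparison would then lean toward RBX2660 even if the product added nothing. Repeating the analysis in the FAS or Per Protocol set cannot reveal this, because both start from dosed subjects. The best-case imputation cannot reveal it either, because undosed subjects are not in the FAS to be imputed.

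**Working it through.** **Who can be counted.** Take a subject who consents, then has persisting CDI diarrhea, is retreated, receives a fecal transplant or dies before the first enema.

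| Set | Undosed RBX2660 subject | Selected control |
|---|---|---|
| Enrolled | in | in |
| Safety | out | not applicable |
| FAS | out | in |
| Evaluable (primary) | out | in if outcome evaluable |
| Per Protocol | out | in if evaluable and no listed exclusion |

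The Evaluable example in SAP 6.3 removes people who left before failure was determined and were not followed for 56 days. A control with an early documented failure has been determined, so that example does not remove it.

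**How large the effect could be.** The readable text gives no expected number of undosed subjects and no visible alpha or test, so there is no planned figure to reproduce. What follows is an illustration.

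Inputs:
- p = 35% recurrence-free, which is 1 minus the 65% recurrence after two relapses in Appendix 1 A3.
- 150 RBX2660 subjects and 100 controls (SAP 4.5). Appendix 1 A7 allows up to 200 controls.
- One-sided 2.5% pooled two-proportion z-test (assumed).
- f = the share of patients who fail before the dosing point and are scored as failures among controls but are absent from the RBX2660 sets (assumed, varied).

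With no drug effect, the control rate is p and the RBX2660 rate among those left is p/(1 − f):
- f = 2%: 0.35/0.98 = 35.7%, a bias of 0.7 points.
- f = 5%: 0.35/0.95 = 36.8%, a bias of 1.8 points.
- f = 10%: 0.35/0.90 = 38.9%, a bias of 3.9 points.

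The false-positive rate is the exact binomial probability that z exceeds 1.96, where z = (x/150 − y/100) / √[p̄(1 − p̄)(1/150 + 1/100)], x and y are the success counts and p̄ is the pooled success proportion.

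| Case | f = 0 | 2% | 5% | 10% |
|---|---|---|---|---|
| p = 35%, 150 vs 100 | 2.5% | 3.2% | 4.8% | 9.0% |
| p = 35%, 150 vs 200 | 2.5% | 3.4% | 5.5% | 11.3% |
| p = 50% (assumed), 150 vs 100 | 2.6% | 3.8% | 6.3% | 14.1% |

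Normal-approximation check at f = 5%, first row: the standard error is 0.0620 under the null and 0.0619 at the shifted rates, so (0.0184 − 1.96 × 0.0620)/0.0619 = −1.67, which gives 4.8%. If 150 counts enrolled rather than dosed subjects, f = 10% leaves 135 dosed and the same approximation gives 8.8%.

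For scale, against 35% in 100 controls, significance needs 72/150 = 48%, a gap of 13 points. A bias of 3.9 points is under a third of that.

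**What an enrolled-based analysis would show.** Suppose 70% of dosed subjects succeed (assumed) and all undosed subjects left for CDI reasons. With 8 of 150 undosed, the rate is 0.70 × 142/150 = 66%. With 15 undosed, it is 0.70 × 135/150 = 63%.

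**The case against.** The strongest reply is that the controls do face a gate. A6.2 item 1 uses the same words as the trial's exclusion 1, and item 2 differs only in tense. If a known history can reach the enrollment course when re-checked at Visit 2, it can also reach a control's analysed course. Appendix 1 A4 also identifies charts through a return of diarrhea after a completed regimen that stopped symptoms. If controls are scored only from the end of their antibiotic course, on-course failures fall outside the outcome window in both arms. The control index course and time zero are not readable, and text is redacted in A4, SAP 4.4, 4.5 and 8.7.1. Finally, a dosed-only set is defensible for an objective about one treatment with RBX2660.

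Much of this stands. It rules out three stronger readings that a reader might infer:

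- *Every selected control is counted.* This holds for the FAS. The primary Evaluable set and the Per Protocol set can both drop controls.
- *Failures before dosing leave one arm only.* This is not shown, because A6.2 items 1 and 2 may remove comparable controls.
- *Recurrence during washout keeps a subject from being dosed.* Protocol 6.5 says only that CDI symptoms are assessed at Visit 2. No readable text bars dosing on that ground.

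Two things survive. A6.2 item 1 is not tied to the control's analysed course, whereas the RBX2660 check is repeated at Visit 2 after the enrollment course. Even with items 1 and 2 fully applied, an RBX2660 subject who dies, receives a fecal transplant or leaves for other treatment before dosing is in no readable efficacy set, and no readable control criterion mirrors that.

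**Conclusion.** The point holds as a gap that the readable analyses cannot detect, not as a demonstrated bias. The readable rules condition the RBX2660 rate on reaching the first enema and set no equivalent condition for controls at the end of the analysed course. Any resulting error favours RBX2660.

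Its size is unknown. The value of f is pure assumption and is net of every control that A6.2 or the Evaluable rule removes, so it is probably small. At or below about 5% the inflation is modest (4.8% against a nominal 2.5% at p = 35%), and at 10% it is material (9.0%). These figures rest on the assumed test, p = 35% and no drug effect. A reader might conclude that the controls have no aligned time zero at all. The documents do not support that, because the relevant text may be redacted.

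**What to change.** 1. In SAP 8.7.1, add one sensitivity analysis on the Enrolled Population, which SAP 6.3 already defines. Count RBX2660 subjects not dosed because of CDI diarrhea, retreatment, fecal transplant or death as non-successes, and omit those not dosed for unrelated ineligibility. Label it a conservative bound, because A6.2 item 1 may already have removed comparable controls.

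2. Report enrolled-but-undosed subjects by reason beside the primary result. SAP 8.1 already counts them, and Protocol 4.4 records the reason for leaving.

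3. Unless redacted text already does so, state that A6.2 items 1 and 2 apply to the control's analysed antibiotic course, and start the control outcome window at a post-antibiotic point equivalent to that of the RBX2660 arm. Do not drop a control only because the chart has no note on that day. Sparse charting would otherwise cost controls against the stated minimum of 100 (Appendix 1 A7).

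The cost is a few sentences and one extra table, with no new data from trial subjects. The RBX2660 advantage may look slightly smaller.

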4.1.3 Definition of Treatment Success

Treatment success is defined as the absence of CDI diarrhea without the need for retreatment with *C. difficile* anti-infective therapy or FT through 56 days after completion of study treatment.

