4.1.4 Definition of Treatment Failure (CDI Recurrence)

Treatment failure (CDI recurrence) is defined as: 1) the presence of CDI diarrhea (see Section 4.1.2), with or without other CDI symptoms, < 56 days after administration of the last assigned study enema; 2) a positive stool test for *C. difficile*; 3) need for retreatment for *C. difficile* infection; and 4) no other cause for CDI symptoms has been determined. [REDACTED]

[REDACTED]

[REDACTED]
[REDACTED]

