6.5 Efficacy Variables

The efficacy variables include the following:

- Treatment success, defined as the absence of CDI diarrhea without the need for retreatment with *C. difficile* anti-infective therapy or fecal transplant (FT) through 56 days after administration of the last study enema.
- SF-36 scores obtained at the 8-week assessments visits as compared to those obtained at the Screening visit.

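### Do the Evaluable Population and the 56-day window need rewriting because the visible SAP does not name the controls' index antibiotic course and day 0?

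*SAP*

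**What the plan says.** SAP 8.7.1 sets the primary analysis: "Treatment success is the primary efficacy endpoint and the analyses will be performed on the Evaluable Population". SAP 6.3 draws that population from the Full Analysis Set, which "includes the Safety Population and subjects in the historical control arm". The rule for being evaluable is given by example. It leaves out subjects who "discontinued from the study prior to determination of treatment failure and were not followed for at least 56 days (day 49 – 63"; the required follow-up is "at least 56 days (day 49 – 63) after the last treatment date".

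The outcome window is worded in several ways. SAP 4.1.3 defines success as no CDI diarrhea without the need for "anti-infective therapy or FT through 56 days after completion of study treatment". SAP 4.1.4 counts failure from the time "after administration of the last assigned study enema". SAP 6.5 runs success "through 56 days after administration of the last study enema".

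For controls, Protocol Appendix 1 (A4) describes a chart review without patient contact. It collects start and stop dates, treatments and outcomes for each CDI episode. It defines a recurrence as starting less than 8 weeks after a CDI treatment regimen was completed.

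SAP 8.7.1 repeats the analysis on the Full Analysis Set and the Per Protocol population. It adds a sensitivity run in which "missing responses are imputed using a best-case scenario where missing responses are treated as successes".

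Text is blacked out in Appendix A4, SAP 4.1.4, 4.1.6, 4.4, 4.5, between 6.1 and 6.3, and in 8.7.1.

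**The concern.** Efficacy is judged only against the historical controls, so their recurrence-free rate carries half of the primary comparison. A control eligible under criterion (a) has had at least three episodes and two completed antibiotic rounds, so several courses could be the index. Two effects arise by construction. A window opened before the recurrence that made the patient eligible counts that recurrence as the failure. A window opened at the last course on file has no later recorded course to count against it. SAP 5.1 says the controls had already been chosen, so a rule fixed late could be fixed with outcomes in view.

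Two smaller points add to this. The example in SAP 6.3 speaks of leaving the study, which a chart cannot do. It also treats a minimum of 56 days as if it were a range that begins at day 49.

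**Working it through.** **1. The plan's own figure.** SAP 4.5 gives up to about 150 treated subjects and 100 controls. Alpha, power and assumed rates are not visible, so this cannot be reproduced. The sizes are used below only for scale.

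**2. Do the anchors conflict for RBX2660?** Protocol 7.2 identifies completion of study treatment with Visit 3, and SAP 4.1 identifies it with the second enema. For a subject who has both enemas, completion of treatment, last assigned enema, last enema and last treatment date are therefore one day.

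**3. What applies to controls?** Only the last treatment date in SAP 6.3 can be read for a control.
- *Day.* Appendix A4 counts recurrence from completion of a regimen over 8 weeks (56 days). By analogy this points to the end of the course.
- *Course.* No visible text names it. The other control dates are not rival starting points: A4 uses the start of data collection to define age, and A6.2 uses its dates for eligibility.
- *Signs that a control treatment date exists.* SAP 6.4.2.4 applies an initial treatment date to the Full Analysis Set, which includes controls (though its partial-date rules speak of the enema). SAP 5.1 describes matching on baseline factors.

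**4. Scale of the course choice.** Assume 65% recurrence per course (Appendix A3, after two relapses), independent courses, and treatment repeated until success or until K qualifying courses are on file.
- First qualifying course: 1 − 0.65 = 35% recurrence-free.
- Last course on file: 1 − 0.65² = 57.75% (K = 2); 1 − 0.65³ = 72.54% (K = 3).

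Power uses a pooled z-test, two-sided 0.05 (assumed), 150 v 100:

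Φ{[p₁ − p₀ − 1.96√(p̄(1 − p̄)(1/150 + 1/100))] / √(p₁(1 − p₁)/150 + p₀(1 − p₀)/100)}

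Example, p₁ = 0.70 and p₀ = 0.5775:
- p̄ = (105 + 57.75)/250 = 0.651
- pooled SE 0.0615, so the critical difference is 0.1206
- unpooled SE 0.0620
- Φ[(0.1225 − 0.1206)/0.0620] = 0.51

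| Control rate | RBX2660 70% | 80% | 85% | 90% |
|---|---|---|---|---|
| 35% | >0.99 | >0.99 | >0.99 | >0.99 |
| 57.75% | 0.51 | 0.97 | >0.99 | >0.99 |
| 72.54% | 0.01 | 0.28 | 0.67 | 0.94 |

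The visible text gives no RBX2660 rate, so no column can be called the plan's. The cap K is also invented. Without it, the last course in a complete chart would be recurrence-free in nearly everyone.

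**5. Day 49 against day 56.** With 35% recurrence-free at day 56 and a constant hazard, the rate at day 49 is 0.35^(49/56) = 39.9%, a gap of 4.9 points. Hazards that fall with time (Weibull shape 0.7 and 0.5) give 3.4 and 2.5 points. These are upper limits, because they need every subject to be last seen on day 49. SAP 6.1 shows Visit 4 at 8 weeks ± 7 days, which is where the bracket comes from. For RBX2660 subjects, later calls assess CDI symptoms, and Protocol 3.7 has every on-study CDI episode recorded.

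**6. Unequal loss.** Let p = 0.35 in both arms, u = share lost, and f = share of would-be failures among those lost that are determined first. The Evaluable rate is p(1 − u)/[p(1 − u) + (1 − p)(1 − u(1 − f))]. With u = 5% for RBX2660 and 20/30/40% for controls (assumed), the false-win chance is:
- 2.5% throughout at f = 0
- 5/8/13% at f = 0.5
- 9/18/32% at f = 1

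The SAP 6.3 example, however, requires both discontinuation and short follow-up. Read literally, a chart control is never dropped, so these scenarios do not follow from it. In simulation, the planned best-case run held the false-win chance at 2.5% or less in all nine cases.

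**The case for a change.** The strongest case for a change needs no model. A single-arm trial with chosen controls should state openly which course and day start the control clock, because the two effects by construction can push the rate towards 0% or 100%. An example is not a derivation rule. Redaction does not remove the visible mismatch between a minimum of 56 days and a range from day 49, and one sentence in the SAP would settle it.

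Part of this stands. The visible text names no index course, and the wording in SAP 6.3 was written with trial participants in mind. If the unredacted SAP were silent too, the point would be a real one.

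The rest does not carry. The failure definition (SAP 4.1.4), the determination of outcome (4.1.6), the description of the control arm (4.4) and the control data list (Appendix A4) all run into blacked-out text, exactly where such a rule belongs. What redaction hides cannot be counted as missing. The first-course, random-course and pre-eligibility readings come from no passage. The remedies on offer ask for an index course and a cut-off day to be named without proposing either. A rule that keeps every documented failure but drops non-failures whose charts end early would build in the very bias modelled in step 6 of the working.

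**Conclusion.** No change to the plan. The RBX2660 anchors agree for subjects who complete both enemas. The day 49 to 63 bracket is the Visit 4 window in loose wording, worth no more than 2.5 to 4.9 points even if everyone is last seen on day 49. The controls' index course and day 0 are not visible, but the text where they would stand is redacted, and the dates needed to derive them are collected for every episode. An analyst would fill this gap from those dates, with the end of the course as the natural counterpart to completion of study treatment.

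The scenario figures show only that the choice could matter. They rest on 65% recurrence per course, independent courses, an invented cap on courses, assumed losses and an assumed RBX2660 rate, and should not be cited as the size of an effect. This conclusion assumes that the unredacted SAP states the control rule. Someone with access to it can confirm that by reading, without amending the plan.

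### The Per Protocol set can drop a documented failure for something that came after the failure, because only the FMT exclusion spares documented recurrences (SAP 6.3)

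*SAP*

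**What the plan says.** SAP 6.3 forms the Per Protocol Population by removing four groups from the Evaluable Population:

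1. "Subjects from the Safety Population that did not complete 2 enemas". The Safety Population is the RBX2660 arm alone: "this does not include subjects in the historical control arm".
2. "Subjects that received fecal microbiota transplant before the 8-week follow-up and lacked a documented recurrence of CDI".
3. Violations of the eligibility criteria.
4. "Received prohibited medication during the 8-week follow-up period".

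The parent set keeps determined failures, since its example is to "exclude subjects that discontinued from the study prior to determination of treatment failure and were not followed for at least 56 days".

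SAP 8.7.1 gives the roles of the sets: "Treatment success is the primary efficacy endpoint and the analyses will be performed on the Evaluable Population", and then "The analysis of efficacy will be repeated using the Full Analysis Set and Per Protocol populations".

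Other provisions that bear on the point:

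- The second enema may be brought forward if diarrhea returns within 7 days (protocol 3.2, SAP 4.1). Antibiotics are not allowed between the two doses (protocol 3.2).
- After a failure, the investigator chooses the therapy (protocol 3.7, SAP 4.1.5).
- The 56-day failure window runs from completion of study treatment in protocol 3.6, but from the last assigned enema in SAP 4.1.4.
- Protocol 5.6, Concomitant Therapy, is in the table of contents, but its text is not visible in the public version. The visible text does not define prohibited medication.

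**The concern.** The FMT item shows that the authors saw the problem in one place: a documented recurrence should not disappear from the analysis because of how it was then treated. The two-enema and prohibited-medication items lack that protection, and both depend on events after baseline that a recurrence can itself cause. A subject whose CDI returns after the first enema, and who is treated another way instead of receiving the second, would leave the Per Protocol set because of the failure.

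The comparison is open-label and non-randomised, with outcome determined by the site investigator. Per Protocol is one of two named repeats of the primary analysis. If it can lose failures from the treated arm by a rule that cannot touch controls, its agreement with the primary result gives less reassurance than it seems to.

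**Working it through.** **Step 1. The exclusions side by side.**

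| Per Protocol exclusion | Arm it can affect | Spares a documented failure? |
|---|---|---|
| Fewer than two enemas | RBX2660 only | No |
| FMT before 8 weeks | Either | Yes |
| Eligibility violation | Either | Settled at entry |
| Prohibited medication in the 8 weeks | Either | No, and no limit on timing relative to failure |

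**Step 2. Who reaches the two-enema exclusion.** A one-enema subject becomes Evaluable as soon as failure is determined. A one-enema subject who does not fail must be followed for about 56 days (days 49–63) to be Evaluable. Failures may therefore be over-represented among those removed, but nothing in the documents fixes the mix.

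**Step 3. Size for the two-enema rule.** The plan states no Per Protocol rate and no expected number of exclusions, and its sample-size assumptions are redacted. There is thus no figure to reproduce, and what follows is illustration. Let N be the number treated, S all successes, s the excluded successes and f the excluded failures:

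Per Protocol rate = (S − s) / (N − s − f)

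N = 150 is the planned maximum (SAP 4.5), with all 150 taken as evaluable. The success rates are assumptions. At 75%, S is an expected count: 0.75 × 150 = 112.5.

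| Assumed success | Excluded failures f | Excluded successes s | Per Protocol rate |
|---|---|---|---|
| 75% | 3 (2% of N) | 0 | 112.5/147 = 76.5% |
| 75% | 6 (4% of N) | 0 | 112.5/144 = 78.1% |
| 75% | 3 | 9 (in proportion) | 103.5/138 = 75.0% |
| 75% | 2 | 10 | 102.5/138 = 74.3% |
| 70% | 5 | 0 | 105/145 = 72.4% |
| 70% | 5 | 12 (about in proportion) | 93/133 = 69.9% |
| 70% | 5 | 15 | 90/130 = 69.2% |

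Over assumed success rates of 65%, 70% and 80%, removing 3 to 10 failures and no successes raises the RBX2660 rate by 1.3 to 5.7 points. The control rate does not move under this rule.

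**Step 4. Direction for the prohibited-medication rule.** Suppose rescue anti-infectives count as prohibited in both arms. Take RBX2660 at an assumed 70% (105 of 150, 45 failures). Take controls at 35 of 100 (65 failures), from the 65% recurrence after two relapses in protocol Appendix 1, A3, and the 100 controls in SAP 4.5. Remove about half the failures in each arm:

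- RBX2660: 105/(150 − 22) = 105/128 = 82.0%
- Controls: 35/(100 − 32) = 35/68 = 51.5%

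Both rates rise, but the difference falls from 70.0 − 35.0 = 35.0 points to about 30.6 points. More control failures are there to be removed, so on this reading the comparison moves against RBX2660.

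**The case against.** The strongest reply is that this is a conventional completer set in a supporting role. Treatment is defined as two enemas, so a set restricted to subjects who had two is ordinary. The primary analysis uses the Evaluable Population, which keeps determined failures, and the Full Analysis Set repeat keeps one-enema subjects. The option of an earlier second enema also steers an early recurrence toward a second dose, so few failures may stop at one. All of this stands and limits the consequence. It does not explain why one exclusion spares documented failures and two do not. The earlier enema is permitted, not required.

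A reader might infer three stronger things that the documents do not support:

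- *That Per Protocol success must equal or exceed the primary result.* The two-enema rule removes successes as well as failures. The rate rises only if failures are over-represented among those removed; it can stay level or fall, as Step 3 shows.
- *That the prohibited-medication rule also favours RBX2660.* It is not limited to one arm, and Step 4 shows that it could narrow the difference. The one-arm argument rests on the two-enema rule alone.
- *That success could be driven toward 100% because retreated failures are deleted.* That needs rescue anti-infectives to be on a list nobody can see in the public text. Therapy that both documents expressly provide for after failure is not naturally read as prohibited.

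It is also not settled that a recurrence after one enema is an Evaluable failure. On a literal reading of protocol 3.6, the clock starts only when both enemas have been given. SAP 4.1.4 starts it at the last assigned enema. Text next to both definitions is redacted.

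**Conclusion.** The point holds in a limited form. As worded, SAP 6.3 lets a documented failure leave the Per Protocol set because of something that followed it. Under the two-enema rule, this can happen only to RBX2660 subjects. The result is a risk of inflated RBX2660 success in a supportive analysis; the primary analysis is not affected.

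A plausible size is 1.5 to 3.1 points (76.5 − 75.0 and 78.1 − 75.0). This rests on an assumed 75% success, on 2–4% of subjects being excluded one-enema failures, and on no successes being excluded. The 2–4% has no source in the documents; at 75% success it means that 2/25 = 8% to 4/25 = 16% of all failures stop at one enema. With proportional exclusion of successes, the shift is about zero. For prohibited medication, the finding is an ambiguity that could affect failures in both arms and could shrink the treatment difference.

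**What to change.** Add to SAP 6.3, for both arms: 'Per Protocol exclusions for incomplete treatment, FMT or prohibited medication apply only to events dated before a documented treatment failure; a subject whose documented failure came first stays in as a failure.' A missed enema has no date of its own, so the SAP should say which date stands for it, for example the end of the visit window (7 + 2 = 9 days after the first enema).

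Two additions go with this:

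- Tabulate Per Protocol exclusions by arm, reason and outcome, so that a reader can see whether failures or successes were lost.
- Reconcile the failure clock in protocol 3.6 and SAP 4.1.4, so that a recurrence after one enema is classified the same way in both documents.

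The cost is a few sentences, a date comparison in programming and one table. The downside should be stated in the SAP. Per Protocol success may be slightly less favourable and, because one-enema successes are still excluded, the rule leans mildly conservative. At an assumed 70% (105/150), keeping all failures while excluding 5 or 10 one-enema successes gives 100/145 = 69.0% or 95/140 = 67.9%.
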